## Background

Transcranial direct current stimulation (tDCS) tDCS is a painless method for focal brain stimulation. tDCS is based on decades-old observations that neuronal firing is modulated by low amplitude electrical direct current (DC). Specifically, when applied to the cerebral cortex, cathodal DC inhibits neuronal firing (Creutzfeldt, 1962, Nitsche, 2000). The mechanisms by which cathodal DC reduces neuronal firing likely relate to hyper-polarization of the soma membrane which occurs when the apical dendrites neurons are oriented toward the cathode in a constant electric field. The practical application of tDCS is simple: low amplitude DC is administered via scalp electrodes such that the cerebral cortex is exposed to cathodal DC beneath one of the electrodes, and the return (anodal) electrodes can be placed anywhere else on the body, or in more complex arrangements to minimize currents at any site. tDCS methods have also recently been adapted to rats for work with disease models (Kabakov 2012, Rotenberg, 2014). Hundreds of tDCS trials have demonstrated the technique to be well tolerated and safe. Direct electrical current stimulation is presently FDA-approved for extracranial use, and FDA applications for cranial stimulation (tDCS) for management of mood disorder and chronic pain are in progress. tDCS units are also inexpensive and lightweight. The electrical supply can be derived from conventional 9-volt batteries. The scalp electrodes can be fastened in seconds. tDCS can be combined easily with other therapies, such as those that may be required for resuscitation of an acutely injured patient. tDCS is presently under investigation as a treatment for epilepsy (IDE attached to this one), where excess cortical excitability is a prominent feature of the disease

process, and where neuronal inhibition may be beneficial. The tDCS stimulator used in this clinical study is the STARSTIM device (Neuroelectronics, Inc). Starstim has an associated software that allows to personalize treatment per pathology and target different brain region.

## tDCS and Depression

Transcranial direct current stimulation (tDCS) delivers weak currents into the brain through two or more electrodes placed on the scalp. When appropriate guidelines are followed, tDCS is safe and extremely well tolerated (Antal et al., 2017). The mechanisms of action remain insufficiently understood but appear to involve polarity-dependent shifts in neuronal membrane potentials, thus leading to purely neuromodulatory effects that modify likelihood of neuroplasticity effects (potentiating or suppression plasticity depending on anodal versus cathodal effects). Notably tDCS effects spread across functional brain networks and thus enable modulation of brain connectivity related to mood disorders and MDD.

There has been a fairly large number of studies, including randomized, sham-controlled clinical trials (RCTs) on the effects of tDCS in MDD. Results have been variable and in part discrepant. For example, Brunoni et al., (2017) found tDCS to have similar efficacy to antidepressant medications, while Loo et al., (2018) found no efficacy of real tDCS over sham in MDD. Nonetheless, several meta-analyses have concluded that tDCS is effective for MDD (Mutz et al., 2018; Brunoni et al., 2016). Most recently, Razza et al. (2020) completed a systematic review of all studies of tDCS for treatment of acute major depressive episodes completed up to January 2020. They included all randomized, sham-controlled clinical trials (RCTs) enrolling participants with an acute depressive episode, a total of 23 RCTs with 1,092 participants. They found that active tDCS was superior to sham regarding endpoint depression scores, response and remission rates. Moreover, active tDCS was safe with a side-effect profile comparable to sham. Moffa et al. (2020) also recently published an individual patient data (IPD) meta-analysis evaluating the efficacy and acceptability of tDCS for treatment of acute major depressive episodes. The IPD meta-analysis is more accurate in estimating the efficacy of an intervention and also superior to the aggregated data approach for obtaining predictors of treatment outcome since it uses the raw data of each participant collected from each study (Riley et al., 2010). Moffa et al. included data from all published placebo-controlled trials on tDCS as only intervention in MDD conducted until December-2018. This included 9 eligible studies with a total of 572 participants. They found active tDCS to be significantly superior to sham for an antidepressant response (30.9% vs. 18.9% respectively; OR = 1.96), remission (19.9% vs. 11.7%, OR = 1.94), and depression improvement (effect size  $\beta = 0.31$ ). Moreover, they found a consistent continuous clinical improvement after the end of the tDCS treatment course. It is noteworthy that the clinical efficacy was substantially higher in the studies where the tDCS course was longer (3-4 weeks versus 1-2 weeks).

The variability in the literature on the antidepressant effects of tDCS may reflect differences in patient selection as well as in the tDCS protocol. Longer courses of treatment seem particularly important to ensure sustained, lasting benefits. Consistent with current understanding of mechanisms of action, tDCS antidepressant effects may involve long-term neuroplastic changes that take time to develop and may in fact continue to evolve and mature even after the tDCS treatment course has ended. This makes long treatment courses with maintenance phases important, and home-based interventions appealing. Importantly, across all studies, active tDCS has been well tolerated and there have been no significant adverse or side effects.

## Home Use of tDCS

tDCS, as a relatively simple and portable technology, is particularly well suited for remotely-supervised, home-based treatment, which would facilitate longer periods of treatment as well as offer a suitable therapeutic option at the present time as we aim to deal with the COVID-19 pandemic.

Several equipment manufacturers have developed tDCS systems for remotely-supervised, home-based use, where the treatment is administered by the patient or a caregiver.

Treatment parameters, scheduling and outcomes can be monitored remotely by clinic or research staff. To date, this has been piloted for treatment of a number of conditions including neuropathic pain (Garcia-Lorrea et al., 2019), auditory hallucinations in schizophrenia (Andrade, 2013), multiple sclerosis (Charvet et al., 2017; Charvet et al., 2018; Kasschau et al., 2016; Kasschau et al., 2015), Mal de Debarquement Syndrome (Cha et al., 2016), Parkinson's disease (Agarwal et al., 2018; Dobbs et al., 2018), trigeminal neuralgia (Hagenacker et al., 2014), vascular dementia (André et al., 2016) and Prader-Willi syndrome (Azevedo et al., 2017) with promising results.

Palm et al. (2018) completed a systematic review of all available evidence on home use of tDCS until May 2017. They identified 22 original research papers, trial protocols or trial registrations involving home-use tDCS, mostly as an add-on intervention to cognitive or physiotherapeutic intervention. Study samples were small, and many were single-blinded studies focused on feasibility and safety. Nonetheless, Palm et al. were able to show that treatment adherence was high and side-effects minimal, and thus they concluded that remotely controlled and supervised home-used tDCS was feasible and promising. The experience with home-use tDCS has continued to grow since then.

In the setting of depression, Clayton et al., (2018) reported a case of one patient with comorbid multiple sclerosis and recurrent depressive episodes who received a course of remotely supervised tDCS following ECT treatment. Fatigue and mood ratings improved. More recently, Alonzo et al. (2019) completed a proof-of-principle, open-label trial in 34 participants who were taught to self-administer 20–28 tDCS sessions (2 mA, 30 min, F3-anode and F8-cathode montage according to 10–20 EEG placement) over 4 weeks followed by a taper phase of 4 sessions 1 week apart. Participants were initially monitored via video link for a few days, and then through completion of an online treatment diary. Participants met criteria for a diagnosis of MDD according to the DSM-IV-TR, as determined via an interview with a study psychiatrist, and confirmed with the Mini International Neuropsychiatric Interview (MINI; Version 5.0.0) (Sheehan et al., 1998). Inclusion criteria included a current major depressive episode of at least four weeks duration as part of a uni- or bipolar depression; and a score of at least 20 on the Montgomery–Asberg Depression Rating Scale (MADRS) at trial entry. Exclusion criteria were any DSM-IV-TR psychotic disorder; drug or alcohol abuse or dependence in the preceding 3 months; concurrent benzodiazepine medication; high suicide risk; history of clinically defined neurological disorder or insult; metal in the cranium or skull defects; skin lesions on the scalp at the proposed electrode sites; and pregnancy. Participants on antidepressant medication were permitted to enter the trial provided the medication dose was unchanged for 4 weeks prior to trial entry and during the acute treatment phase of the study. One participant was withdrawn from the study due to too many missed sessions. The remaining 33 participants completed 93% of the scheduled sessions in the initial 4-week phase. Ten of thirteen participants (77%) who qualified for the maintenance phase opted to continue. Mood improved significantly from baseline (27.5 on MADRS) to 1 month after the end of acute treatment (MADRS 15.5;  $p < 0.001$ ). Side effects reported across a total of 1,149 sessions were minimal, primarily mild to moderate tingling or burning/heat sensation during stimulation and redness at the electrode sites. This study provides clear, initial evidence that home-based, remotely supervised tDCS treatment is feasible for depressed patients and offers a potentially effective intervention.

## Process of Consent

Potentially eligible individuals (Participants with MDD and their participant caregiver-administrators) will each be emailed or snail-mailed (per request, and according to their preference) a copy of the informed consent for them to review at their own pace prior to the telephone screening call. Written or verbal informed consent will be obtained by study personnel at the beginning of this in-person screening call, depending on the ability of the research team to have personal contact due to the restrictions imposed by COVID-19 precautions.

## Home-use device and training to caregivers

Alonzo et al. (2019) used a tDCS device that required the placement of individual, large sponge electrodes onto the scalp in positions defined by the 10-20 EEG electrode placements (F3 and F8). The large sponge electrodes needed to be held in place by elastic bands. The procedure posed substantial challenges and precluded some caregivers from achieving appropriate level of competency. In addition, the interface with a programmable device for specification of stimulation parameters was challenging and again represented a hurdle for some patient-caregiver pairs.

Neuroelectrics has developed a system for home-based tDCS that effectively overcomes these challenges and is being used in several studies, e.g. Garcia-Lorrea 2019 (<https://clinicaltrials.gov/ct2/show/NCT02346396>). The Starstim Home Kit® (Neuroelectrics Corp) is commercially available and approved in Canada for use in treating chronic pain, depression and addictive disorders. It utilizes the company's industry leading Starstim system, with additional features that enable researchers and clinicians to "prescribe" and monitor home-based tDCS to end users. Briefly, the Starstim system resembles a swimming cap that fits loosely on the head, but with small electrodes that lie on the scalp and deliver low-level electrical currents to targeted brain regions. Within the Home Kit, the relevant electrode positions are marked on the headcap with different colors and numbers, and the corresponding electrode leads (cables) from the tDCS device are marked with the same colors and numbers. This ensures that the user places the electrodes in the correct position and secures the correct lead to each electrode. The Home Kit also utilizes a tablet that provides the user with step-by-step instructions to set up the Starstim device, check electrode impedance, and record side effects. The user may also videoconference with remote staff in real-time. The researcher uses Neuroelectrics online Portal (NE Portal) to remotely schedule sessions and monitor in real-time specific treatment events to ensure safety.

At the Marcus Institute we have developed a training and in-home supervision program to accompany the Starstim Home Kit and have established its feasibility in two ongoing studies (one focused on gait and balance and the other on episodic memory in dementia). In these studies, to date we have completed the assessments of eight participant 'pairs;' that is, an individual to receive tDCS along with a family member, friend, or care-giver willing and able to administer tDCS. Each potential administrator was initially screened to ensure that they would be available throughout the intervention period and to ensure they had at least minimal computer proficiency. They were then trained by staff to administer tDCS to the study participant and did so under the supervision of staff until they self-reported comfort in the process and were deemed proficient as determined with a custom-developed checklist. For all eight participant-pairs, the administrators, who ranged in age from 44 to 87, achieved proficiency by the third session of tDCS. All but one pair completed at least eight sessions of the 10-session intervention. No adverse events were reported. Transient skin redness and tingling sensations under the electrode were the only reported side effects and the frequency and severity of these side effects were similar to that reported in published staff-administered interventions. Upon exit interview, all administrators—and the participants who received the stimulation—stated that the Home Kit and training materials were easy to use, that

they were satisfied with the experience and training they received, and that they would be willing to use to system again in the future.

The above studies utilize in-person training methods until the participant administrator achieves proficiency. For the current proposal, a video telemedicine-based training program is available to ensure minimal staff-participant contact. Moreover, a pre-configured Starstim system will be shipped directly to the participants with all the required supplies and documentation.

Eligibility Criteria: Patients meeting one of the following criteria may be eligible to participate in this study.

1. Patients with medication-resistant MDD who have undergone rTMS or ECT and responded to it but whose benefit has lapsed, and they need repeat a rTMS or ECT course that they cannot access
2. Patients with medication-resistant MDD who have undergone rTMS or ECT and responded to it but whose benefit has lapsed, and they need repeat a rTMS or ECT course that they cannot access
3. Patients with medication-resistant MDD who are undergoing rTMS or ECT and responding, but cannot continue to get the rTMS or ECT course due to COVID-19 pandemic-related regulations or other access concerns
4. Patients with medication-resistant MDD who are referred to rTMS or ECT and are found well qualified but cannot access rTMS or ECT due to COVID-19 pandemic-related regulations or other access concerns.

The benefits of this project address a present need due to the COVID-19 pandemic, but also go beyond the present situation and address a larger, pre-existing need. Across all these potential groups of participants, prospective participants will:

- need to have a primary psychiatrist who agrees to their participation in the study and is willing to continue to follow the patient and work collaboratively with the study team
- need to be assessed by their primary psychiatrist to be stable enough to be able to remain at home and participate in the present study without undue risk to their safety
- need to be living with an adult willing and capable to provide oversight and learn to deliver the home-based tDCS
- have the capability to connect with the study team for daily supervision of the intervention sessions and close safety monitoring, and be willing to commit to doing so

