At present, given the COVID-19 pandemic and the required and appropriate restrictions on individual mobility and outpatient medical encounters and procedures, access to rTMS, ECT, or similar in-clinic treatments is much more limited. These added difficulties to access ECT and rTMS are occurring at a time when the risk of mental health problems and of decompensation from pre-existing depression is extremely high due to the uncertainties, fears, and stressors caused by the COVID-19 pandemic and the social distancing. The risk of mood and mental health decompensation in the setting of social isolation and loneliness is particularly high among the elderly, who in turn are at a particularly high risk of serious complications of an infection with COVID-19 and thus are faced with particularly high stress, fears, and strict isolation regulations.

Therefore, the current COVID-19 pandemic makes the need for a safe, effective, home-based intervention for an acute, medication-resistant episode of uni- or bi-polar MDD particularly urgent. Transcranial direct current stimulation (tDCS) offers a suitable and readily available solution.

**Study design and purpose:** We propose a safety/feasibility study designed to determine whether it is possible for transcranial direct current stimulation (tDCS) interventions to be successfully delivered by a caregiver at the homes of adults who have medication-resistant MDD.

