Daily sessions (28 daily sessions): The device will be used to apply 20 minutes of tDCS to the participant with MDD's scalp in each of 28 daily sessions.

Thereafter, participants with MDD will undergo a taper phase of an additional 9 sessions of tDCS applied in progressively decreasing frequency until day #60 of the study as follows:

- (1) First taper phase: three 30 minutes tDCS sessions applied every other day;
- (2) Second taper phase: three 30 minutes tDCS sessions applied one every third day;
- (3) Third and final taper phase: three final 30 minutes tDCS sessions applied one every fourth day.

The study team will predetermine, with the participant team, their most convenient two hour window for the home administration. During remote tDCS administration, the study team will be notified electronically by email when the tDCS session has been started and also when it has been completed, or if the tDCS session was aborted, or not completed during the predetermined two hour window.

The device will contain a sequence of simplified screen prompts for the participant,. To move to the next screen the participant will press a circle on the screen to continue (or to stop)

For example:

1. Hello
2. Battery status is GOOD
3. Today is Monday (date) It is now ( ) o'clock
4. Wear the Cap

5. Check the electrodes - 1 green is in the 1 green hole and secure, 2 yellow is in the 2 yellow hole and secure.
6. Are you ready for your 30 minutes session? If yes, press continue
7. Session has started, please stay in place until session is over [clock appears on screen to count down the minutes]
8. Session has ended, please stay in place while the device powers off.
9. Session is now completed! You may turn off the tablet, and remove the cap and electrodes

Daily sessions (28 daily sessions): The device will contain a block that will only allow one session to be administered within a 24 hour period. If a session is started and aborted, the participant will not be able to administer a new session until the next day, 24 hours later.

During the taper phase - the device block will only allow:

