## Statistical Methods and Analysis

### *Primary*

Feasibility and tolerability/safety will be evaluated using home-based data as it is collected by reported number of aborted sessions.

The *primary outcome* will be change in the observer rated MADRS score from baseline to the 1-month follow-up.

Clinical response is defined as  $\geq 50\%$  improvement in MADRS score from baseline to the 1-month follow-up. Remission is defined as a MADRS score  $\leq 10$ .

The *secondary outcome* measures will include the participant-rated Quick Inventory of Depressive Symptomatology (QIDS-SR) (Rush et al., 2003) and the Quality of Life Enjoyment and Satisfaction Questionnaire Short Form (Q-LES-Q-SF) (Endicott et al., 1993), both administered at the same time points as the MADRS. A computer-based cognitive test battery, CogState (<https://www.cogstate.com>), will provide an additional safety outcome measure. This battery includes tests designed to assess verbal learning and memory (International Shopping List Task), attention and psychomotor function (Detection Task), visual attention (Identification Task), visual learning and memory (One Card Learning Task), working memory (Two Back Task), and executive function (Set Shifting Task).

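### A count of aborted sessions cannot show whether the completed home sessions were adequately delivered

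*Combined protocol and SAP*

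**What the plan says.** The study design paragraph under Purpose of the study asks whether it is possible for tDCS "interventions to be successfully delivered by a caregiver at the homes of adults who have medication-resistant MDD". What counts as successful delivery is not defined there or later.

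Under Statistical Methods and Analysis, Primary, one sentence covers the feasibility analysis: "Feasibility and tolerability/safety will be evaluated using home-based data as it is collected by reported number of aborted sessions".

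The section Home-use device and training to caregivers explains how correct use is supported. The system "resembles a swimming cap that fits loosely on the head". Electrode positions and leads carry matching colours and numbers, and of this the text says: "This ensures that the user places the electrodes in the correct position and secures the correct lead to each electrode". The tablet also guides the user to "check electrode impedance, and record side effects", and staff follow certain treatment events live through an online portal. The events are not listed.

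The Visits section schedules video for the sessions on Days 1 to 5, with a staff-administered skills test on Day 5. From Day 6 and through the taper, staff monitor remotely and video is used only when needed. Staff are told by email when a session starts, completes, is aborted, or is not completed in its two-hour window. The example screen sequence includes the prompt "Check the electrodes - 1 green is in the 1 green hole and secure, 2 yellow is in the 2 yellow hole and secure". The list of assessments and forms names a training manual and a caregiver competency checklist, whose contents are not in the text.

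**The concern.** An abort count records that a session stopped early. It says nothing about the quality of the sessions that did not stop. Delivery quality matters here because the protocol itself reports that, in the earlier home study, placing electrodes on the scalp was hard enough to keep some caregivers from becoming competent. It then says that the present kit overcomes this. A feasibility study is the natural place to test that statement, and the planned measure cannot do so.

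Two things are at stake. Feasibility may look better than it was. And if the change in MADRS is small, the trial will have no planned data to help separate stimulation that did not work from stimulation that was not properly given. The protocol's stated goal is to prepare a randomised trial, whose designers will need that distinction.

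**Working it through.** The plan gives no figure for delivery quality, so there is nothing to reproduce. The check has four steps.

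**1. Sessions and scheduled video (Visits section).** Daily sessions: 28. Taper sessions: 3 + 3 + 3 = 9. Total: 28 + 9 = 37 per participant. Scheduled video covers Days 1 to 5, so 5 sessions. Remaining: 37 − 5 = 32, and 32/37 = 86.5%. These 32 have remote staff monitoring, with video only when needed. The fraction does not depend on the sample size. That is convenient, because the Sample Size section does not say whether its 50 counts patients only or both members of each pair.

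**2. What each source of information could show, and whether it is analysed.**

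| Source | What it could show about a completed session | Named in the feasibility analysis? |
|---|---|---|
| Aborted-session count | Only that the session was not aborted | Yes, and it is the only one |
| Start, completion and window emails | That the session ran, and when | No |
| Tablet impedance check | Electrode contact; no limit or stored value is stated | No |
| Portal monitoring | Unlisted treatment events | No |
| Day 5 skills test | Caregiver skill on one day; no pass mark in the text | No |
| Staff monitoring and video after Day 5 | Not specified | No |

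**3. Sensitivity of the planned measure.** Let m be the unknown share of the 32 sessions that ran to the end with inadequate delivery. Suppose that all 37 sessions were completed and the 5 video sessions were adequate. Then the adequately delivered share is (5 + 32(1 − m))/37 = 1 − (32/37)m. The aborted-session count is 0 whatever m is. The share falls as m rises and the count does not move, so m cannot be recovered from it. The documents give no value of m, and I do not assume one.

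**4. Is a full session defined?** The text after the visit table gives 20 minutes for each of the 28 daily sessions. The visit table gives 30 minutes for Days 1 to 5, and the example screen prompt also says 30. Since 20/30 = 67%, a 20-minute run is complete under one statement and two-thirds complete under the other. A log-based measure cannot be computed until these are reconciled.

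**The case against.** The strongest reply is that the plan has many safeguards for delivery besides colour coding: supervision until the caregiver is proficient without coaching, the Day 5 test, remote staff monitoring of every later session, adherence follow-up by video and telephone, the impedance check, the manual and the checklist. All of this stands. It bears on how well sessions are likely to be delivered. It does not put any measure of delivery into the analysis.

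Several stronger readings are tempting, and the documents do not support them:

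- *That the plan counts every session not aborted as a success.* No section says so. Success is undefined, and the analysis names a count, not a pass rule.
- *That the device has no impedance step because the screen prompts omit it.* The prompts are simplified and introduced as an example, and the device description says the tablet covers impedance.
- *That cap position goes unchecked.* A loose cap with correctly matched leads could still be shifted, but the manual and checklist may address alignment and their contents are not in the text.
- *That a particular number of sessions would be misdelivered.* Any such number would rest on an invented rate.

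The abort count might also catch some poor contact if the device stops itself when contact is lost. The documents do not say whether it does.

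**Conclusion.** The point holds in a limited form. The stated feasibility measure cannot tell adequate from inadequate delivery among completed sessions, and delivery information that the protocol already describes is left out of the analysis. The gap matters most for the 32 of 37 scheduled sessions (86.5%) without scheduled video, although those sessions are not unmonitored. How often delivery is poor is unknown, so neither the size nor the existence of any overstatement of feasibility can be shown. The conclusion rests on the analysis section as written and on the attachments adding no further analysed measure. The claim that markings ensure correct position sits in a background description, and rewording it would change no analysis.

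**What to change.** In Statistical Methods and Analysis, Primary:

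- Replace the aborted-session count as the sole feasibility measure with the proportion of scheduled sessions, overall and per participant, that the device log shows ran for the full programmed time and current, with the impedance check passed where the kit stores that result.
- Keep the aborted-session count beside it, and report the Day 5 skills-test result.
- Before this, reconcile the 20-minute and 30-minute session lengths in the Visits section, so that full programmed time has one meaning. The text reviewed does not state this study's programmed current, so the definition should cite the document that does.
- Label any display of MADRS change against delivered sessions as descriptive. Without a control group it is confounded, for example because patients who are doing poorly may complete fewer sessions.
- State as a limitation that impedance and current logs verify contact and delivery, not where the cap sat on the scalp. A shifted cap with good contact would still pass.

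The cost is revised analysis wording and a log export, with no new visits and no change in sample size. Whether the kit stores impedance results is not stated, so that component is conditional. The feasibility figure may come out less favourable than an abort count would suggest.
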